2.1 Participants

40 healthy older adults

2.2 Study type

Monocentric study at the faculty of Movement and Rehabilitation Sciences, observational study, academic study.

2.3 Measurements

- Screening tests to evaluate motor and cognitive function
- Clinical measuring scales for the evaluation of balance
- Task that requires weight-shifting
- Measurements of cortical activity by means of functional Near-Infrared Spectroscopy (fNIRS)

2.4 Duration experiments

One session of \pm 3.5 hours, including 25 min of training, and one session of \pm 1.5u. There will be a period of 24 hours between both sessions.

2.5 Location experiments

Faculty of Movement and Rehabilitation Sciences (KU Leuven).

3 Background and rationale

In 2015, about 900 million people in the world were aged 60+. By 2050, this population will increase up to more than 2 billion¹. Older people show deficits in balance control² and dynamic weight shifting, as more time is needed to perform weight-shifts and the movement becomes less fluent and accurate³. In addition, mediolateral weight-shift performance has been linked not only to ageing, but also to balance and falls^{4, 5}. An observational study even showed that incorrect weight-shifting accounted for 41% of falls⁶, making it one of the main causes of falls in the older population. Previous work reported prevalence rates of 33% up to 50% of healthy older adults who fall at least once a year^{7, 8}. Falling has serious consequences for quality of life and mortality⁹. As such, investigating potential methods to delay or reduce falling is of utmost importance to prevent immobility and a sedentary lifestyle in healthy ageing.

Studying the neural basis of whole body movements is of great importance to increase our insight of gait and balance. The gold standard method is functional Magnetic Resonance Imaging (fMRI) during motor imagery of stance, which identified increased Blood Oxygenation Level Dependent (BOLD) activity in the brainstem, basal ganglia, cerebellum and cerebral cortex during 'postural control'¹⁰. A major drawback of brain scanning is that it occurs in a supine position. In contrast, functional near-infrared spectroscopy (fNIRS) allows measuring brain activity while being upright, albeit at a much lower temporal and spatial resolution¹¹. However, mobile fNIRS systems now permit a wider brain coverage than hitherto possible to examine the neural correlates of postural stability, at least at the cortical level. fNIRS has also been validated against fMRI¹², is more resistant to head motion compared to other EEG¹² and is feasible for use in older adults^{13, 14}.

Recent systematic reviews showed that postural control in older adults can be improved with training¹⁵. However, little is known about the ability and maintenance of re-learning to weight-shift, let alone about its underlying mechanism. Therefore, the primary aim of this project will address this lacuna by studying the effects of training in weight-shifting performance in older adults and its underlying neural imprint. As our previous study (unpublished) showed that adding an extra cognitive task in a so-called dual-task (DT) negatively affects weight-shifting performance, a secondary aim will be to test whether weight-shift training will enhance performance during such DT conditions. The results of this study might form a basis for future technology-based rehabilitation programs.

4 Study objectives

The effects of postural learning on cortical activity have not been identified yet in older adults. During non-postural tasks, older adults needed greater activity and recruited more brain areas during automatization compared to young adults. This is suggested to be the primary reason for impaired motor automaticity with age¹⁶. We will use fNIRS to examine postural learning in the upright position for the first time in older adults. More specifically, we will investigate:

1. Changes in brain activity in frontal, (pre-)motor, and parietal regions associated with the acquisition and consolidation of weight shifting in older adults. In addition, as moving the Centre of Mass (CoM) deliberately also loads sensorimotor function, we will include the parietal cortex as region of interest.
2. Changes in brain activity in frontal, (pre-)motor, and parietal regions associated with the acquisition and consolidation of weight shifting compared to no training (control group).
3. Changes in brain activity in frontal, (pre-)motor, and parietal regions associated with the transfer of single-task acquisition and consolidation of weight shifting to dual-task weight shifting performance.

5 Methodology of the research

5.1 Participants

In total, 40 subjects will be recruited aged 65+. Inclusion criterion include being able to independently stand upright > 5 min. Exclusion criteria are: (a) history of neurological disorders; (b) balance impairments (i.e. vestibular disorders); (c) cognitive impairment (Mini Mental State Exam (MMSE) < 24); (d) visual impairment precluding following of visual targets or colour-blindness as measured with the Ishihara test for color deficiency; (e) chronic musculoskeletal (e.g. osteoarthritis, osteoporosis), cardiovascular (e.g. hypertension, peripheral vascular disease) and respiratory (e.g. chronic obstructive pulmonary disease) disease, as well as diabetes related polyneuropathy.

For this study, 40 healthy older adults will be included. Our previous fNIRS study (unpublished) revealed that our primary outcome, weight-shifting speed, improved from $0,0668 \pm 0,0255$ m/s to $0,0916 \pm 0,0350$ m/s. Based on Caljouw et al.¹⁷, we expect a training effect size of 20%, resulting in a weight-shifting speed of $0,1094 \pm 0,0418$ m/s. Applying a power of 80% and alpha of 0.05 for a repeated measures ANOVA with a within-between interaction design (within: pre vs post: between: training vs control) we calculated a total sample size of 40 participants (20 per group). Considering possible data exclusion due to fNIRS measurements, the collected fNIRS data will be monitored during recruitment, and recruit more participants if necessary.

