Fig. 3B shows that the player is in the middle of an area infested by wasps. By moving the CoM (displayed by the red dot) towards a pre-defined 80% of the fLOS, a water stream will come on to hit the wasp. The number of wasps hit, weight-shifting accuracy, comprising the CoM traject and target deviation, and speed are used as outcomes. The WASP-ST involves hitting wasps in the ML direction by shifting weight. **Fig. 3C** illustrates the WASP-DT. Participants have to perform a serial subtraction task as the secondary task, whereby the red ball (representing the CoM) will change color from red to white and white to red within a random interval between 2-5 seconds. A starting number will appear on the screen for 1.5 sec at the beginning of each trial. Every time the ball changes its color, subtractions have to be made in threes. Subjects will indicate the correct number afterwards, so as not to disturb the fNIRS recording.

5.3.2 *Study specific procedures*

On day 1, subjects in the training group will receive the WASP-training, consisting of 10 blocks of 2.5 minutes. Training will be adjusted to the individual fLOS targeting at least 80%. Before and after training, weight shifting ability will be assessed using the WASP-tests with and without serial subtractions. We will measure cortical activity with fNIRS during weight-shifting following recent guidelines¹¹. We propose a block design distinguishing periods of quite stance from weight shifting. Participants will undergo two blocks offered in a fixed order: I) WASP-ST; II) WASP-DT. Each block has a duration of 4m40s, starting with 20s quiet stance, followed by 20s weight-shifting, alternating in seven trials. This block design allows for the 4s-7s delay in the hemodynamic peak response by having sufficiently long periods of task exposure. Subjects are not allowed to speak, so as not to disturb the fNIRS signal. In the DT-condition, subjects will be asked to focus on the primary and secondary tasks equally. Subjects in the control group will not receive any form of training. Retention tests will occur on day 2 (24 hr). Also, simultaneous fNIRS measurements will be carried out. fNIRS was found to have adequate test-retest reliability¹⁸. Cap placement will be marked to facilitate accurate placement on day 2.

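### The 80% power stated for N = 40 and a 20% training effect depends on inputs the protocol does not give; for the contrast its figures imply (0.0178 m/s), power is 36% at pre-post correlation 0.5 and 81% at 0.9

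*Protocol*

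**What the plan says.** Protocol section 5.1 sizes the trial on weight-shifting speed. The SAP, under Primary outcome, also names speed as the primary behavioural outcome. In the sponsor's earlier unpublished study, speed "improved from $0,0668 \pm 0,0255$ m/s to $0,0916 \pm 0,0350$ m/s". For the new trial the protocol says "we expect a training effect size of 20%, resulting in a weight-shifting speed of" 0.1094 m/s (SD 0.0418). The test is described as "Applying a power of 80% and alpha of 0.05 for a repeated measures ANOVA with a within-between interaction design", with factors "within: pre vs post: between: training vs control", and the result is 40 participants, 20 per group.

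On controls, section 5.3.2 says "Subjects in the control group will not receive any form of training", and section 5.3.1 says the same. Neither document gives a pre-post correlation, expected control means, or the effect size entered. The SAP as supplied has no sample-size calculation.

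**The concern.** Power for a group-by-time interaction depends on the difference between groups in change and on the SD of that change. The first needs the control course and the second needs the pre-post correlation. Section 5.1 gives neither, so its 80% cannot be checked as written, and plausible inputs lead to very different answers.

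The trained mean and SD are both the earlier study's second value multiplied by the same factor. That suggests the 20% is meant over and above 0.0916, which is a small contrast against these SDs. If so, the chance of missing the effect could be well above the 20% that the plan implies. If controls were instead assumed not to improve, the 80% holds, but for a much larger effect than the one described. Either way, a reader cannot tell what difference this trial can detect on its primary behavioural outcome.

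**Working it through.** **Inputs from protocol 5.1.** Means (SD): 0.0668 (0.0255), 0.0916 (0.0350), 0.1094 (0.0418) m/s; 20 per group; alpha 0.05, taken as two-sided because that is what the ANOVA F test gives. **Assumed, because not stated:** correlation ρ and control course, both shown as ranges.

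**Step 1: the contrast.** 0.1094/0.0916 = 1.194 and 0.0418/0.0350 = 1.194. The trained value is therefore the earlier second value scaled up, and the inferred contrast is 0.1094 − 0.0916 = 0.0178 m/s (19.4%; an exact 20% would be 0.0183).

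**Step 2: reproducing N = 40.** Common SD of the two post values: √[(0.0350² + 0.0418²)/2] = 0.03855. So d = 0.0178/0.03855 = 0.462. For a within-between interaction with two time points, λ = f² × N × 2/(1 − ρ), with 1 and N − 2 degrees of freedom.

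- f = d/2 = 0.231, ρ = 0.5, N = 40: λ = 8.53, power 81.2%. At N = 38 it is 79.1%, so 40 is the smallest even total that reaches 80%.
- d/2 is the effect size for a difference between two groups at one time point. In a 2×2 interaction with equal baselines only one of four cells differs, the interaction effects are ± a quarter of the difference, and f = d/4 = 0.115. Then λ = 2.13 and power is 29.6%.

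**Step 3: power for the inferred contrast.** The 2×2 interaction is equivalent to a t-test on change scores (df 38). Within each arm, change variance = s₀² + s₁² − 2ρs₀s₁, averaged over arms. The noncentrality is 0.0178/(SD of change × √(2/20)).

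Example at ρ = 0.5, both arms starting at 0.0668:
- control: 0.0255² + 0.0350² − 0.0255 × 0.0350 = 0.000983
- training: 0.0255² + 0.0418² − 0.0255 × 0.0418 = 0.001332
- SD of change = √0.001157 = 0.0340; noncentrality = 0.0178/(0.0340 × 0.3162) = 1.65; power 36%.

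| ρ | Both start at 0.0668 (SD 0.0255); controls reach 0.0916 | Both start at 0.0916 (SD 0.0350); controls stay there |
|---|---|---|
| 0 | 22% | 18% |
| 0.5 | 36% | 32% |
| 0.7 | 51% | 48% |
| 0.8 | 63% | 64% |
| 0.87 | 75% | 81% |
| 0.9 | 81% | 89% |

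In the first column, total N for 80% power is 118 at ρ = 0.5, 78 at 0.7, 60 at 0.8 and 40 at 0.9. (The 36% here and the 30% in step 2 differ because step 2 uses 0.03855 at both times.)

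**Step 4: controls flat at 0.0668.** The contrast is 0.1094 − 0.0668 = 0.0426 m/s, which is 64% of 0.0668 and 2.4 times 0.0178. At ρ = 0, power is 81% (control post SD 0.0350) or 86% (SD 0.0255). At ρ = 0.5 it is 97-99%.

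**Step 5: difference detectable at 80% power**, SDs as in the first column: 0.031 m/s at ρ = 0.5, 0.025 at 0.7, 0.022 at 0.8, 0.018 at 0.9.

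**The case against.** A reader might infer that N = 40 is irreproducible, or that the trial is shown to be underpowered. The documents support neither. N = 40 comes out in three ways: the 0.0178 contrast at correlation 0.9; flat controls with post SD 0.0350 at correlation 0; and f = d/2 at correlation 0.5. What stands is that each route needs something section 5.1 does not say.

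Four further objections deserve weight.

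- **The contrast is inferred.** The protocol never writes 0.0178 m/s. It is the natural reading of the scaling, but the first column of the table has untrained controls rising 37% (0.0248/0.0668), which no section states.
- **The correlation is unknown in both directions.** Pre and post are the same task on the same day, so a high value is possible. SD choices also matter: using 0.0255 throughout, 80% is reached at about 0.71.
- **The planned analysis is richer.** Protocol 6.2 and the SAP's Main analysis specify a mixed model over pre, post and retention, with possible covariates. As an illustration, suppose the gain is fully retained and all correlations are equal. Comparing the mean of post and retention with pre then gives 50% at 0.5, 65% at 0.7, 76% at 0.8 and 82% at 0.85. That narrows the shortfall but does not remove it at 0.5-0.7. The sample-size paragraph itself rests on pre versus post.
- **No text plans to read a null result as absence of effect.** That is right, so no such misreading is charged to the plan.

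**Conclusion.** The point holds as a reporting gap that bears on the power claim. Section 5.1 claims 80% power for a 20% effect. With the stated SDs and the inferred 0.0178 m/s contrast, its pre/post design delivers this only at a correlation of about 0.87-0.90. At 0.5 power is about 32-36%, and at 0.7 about 48-51%. The alternative that rescues the 80%, flat controls at 0.0668, changes the effect to 0.0426 m/s.

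The exact match at f = d/2 with correlation 0.5 makes it likely that a single-time-point effect size was entered as an interaction effect size. This is an inference from the match; the protocol does not say what was entered.

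The conclusion rests on a two-sided 5% test, a two-time-point comparison and no data loss. The true correlation and control course remain unknown. Worth fixing; confidence is medium.

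**What to change.** Keep N = 40 and revise protocol section 5.1 to:

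1. State the assumed pre and post means and SDs in each group, including what untrained controls are expected to do.
2. State the pre-post correlation, from the sponsor's earlier study if it can be obtained there and otherwise as a range, and the interaction effect size entered.
3. Replace the 80% with the power those inputs give for the 20% effect. If flat controls were meant, describe the effect as 0.0426 m/s (64%) instead.
4. Add the difference detectable at 80% power: about 0.031 m/s at correlation 0.5, 0.025 at 0.7, 0.018 at 0.9.

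If power is instead restated for the planned three-time-point model, the retention assumption and correlations should be given as well.

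The cost is protocol wording and, if the data allow, one correlation from an existing study. No participants are added. The downside is that the stated power for the 20% effect becomes less favourable unless the correlation is about 0.9.

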5.2 Recruitment

Healthy older adults will be recruited based on the age-criterion, i.e. 65+ years. We will announce our study on websites and pin boards reaching older adults (e.g. seniorama, Universiteit Derde Leeftijd, gym clubs, etc.). When interested, potential participants will be provided with the information folders (either via e-mail or regular mail) to present the necessary information in writing. A follow-up conversation will follow, either via telephone or at the candidates' home if preferred. During this conversation the study goals and protocol of the study, as described in the informed consent forms, will be explained thoroughly to make sure everything is clear for the possible participant and allowing him/her to ask questions and make an informed decision. The researchers responsible for testing will execute this recruitment process. The flyers and information folders can be found in the respective files.

5.3 Experimental procedure

5.3.1 General procedures

Design

Participants will be randomly allocated to the training and control groups. The control group will not receive any form of training. Randomization will be computer-generated and blocked in groups of four to achieve optimal distribution in each training arm. The study will have a repeated measures design with two test sessions on two consecutive days.

Motor and cognitive screening

We will collect data on fall frequency, Mini-Balance Evaluation System (Mini-BESTest), and Falls Efficacy Scale. The cognitive assessment will consist of Montreal Cognitive Assessment and specific tests for visuospatial and attention.

Weight-shifting task

Before starting the weight-shifting task (WASP task), functional limits of stability (fLOS) will be assessed by asking the subject to move the Centre of Mass (CoM) as far as possible over its base of support (**Fig. 3A**) in eight different directions by pushing a virtual bar away from the center position. Mean CoM shifts will be calculated and used for personalized scaling of the WASP. Only weight-shifting in the ML direction will be tested and trained to avoid motion artefacts during fNIRS data collection, and because ML weight-shifting in particular has been linked to balance and falls^{4,5}. The WASP task (**Fig. 3B**) was developed and piloted to meet the requirements for balance training for older people in a PhD project under supervision of [name] (De Vries A, 2018). Pilot data showed that the WASP is feasible for use in older adults and can capture fluency of motion as a learning outcome.

Figure 1: (A) Functional limits of stability; (B) Weight shifting task in ST. Red ball is CoM; (C) WASP + serial subtraction in DT

Fig. 3B shows that the player is in the middle of an area infested by wasps. By moving the CoM (displayed by the red dot) towards a pre-defined 80% of the fLOS, a water stream will come on to hit the wasp. The number of wasps hit, weight-shifting accuracy, comprising the CoM traject and target deviation, and speed are used as outcomes. The WASP-ST involves hitting wasps in the ML direction by shifting weight. **Fig. 3C** illustrates the WASP-DT. Participants have to perform a serial subtraction task as the secondary task, whereby the red ball (representing the CoM) will change color from red to white and white to red within a random interval between 2-5 seconds. A starting number will appear on the screen for 1.5 sec at the beginning of each trial. Every time the ball changes its color, subtractions have to be made in threes. Subjects will indicate the correct number afterwards, so as not to disturb the fNIRS recording.

5.3.2 *Study specific procedures*

On day 1, subjects in the training group will receive the WASP-training, consisting of 10 blocks of 2.5 minutes. Training will be adjusted to the individual fLOS targeting at least 80%. Before and after training, weight shifting ability will be assessed using the WASP-tests with and without serial subtractions. We will measure cortical activity with fNIRS during weight-shifting following recent guidelines¹¹. We propose a block design distinguishing periods of quite stance from weight shifting. Participants will undergo two blocks offered in a fixed order: I) WASP-ST; II) WASP-DT. Each block has a duration of 4m40s, starting with 20s quiet stance, followed by 20s weight-shifting, alternating in seven trials. This block design allows for the 4s-7s delay in the hemodynamic peak response by having sufficiently long periods of task exposure. Subjects are not allowed to speak, so as not to disturb the fNIRS signal. In the DT-condition, subjects will be asked to focus on the primary and secondary tasks equally. Subjects in the control group will not receive any form of training. Retention tests will occur on day 2 (24 hr). Also, simultaneous fNIRS measurements will be carried out. fNIRS was found to have adequate test-retest reliability¹⁸. Cap placement will be marked to facilitate accurate placement on day 2.

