5.4 Equipment

Postural outcomes will be measured on the Computer Assisted Rehab Environment (CAREN) (Motek Medical BV, Amsterdam) with integrated force plates. Spherical reflective markers placed bilaterally on anatomical landmarks will allow 3D-kinematic analysis with 7 MX-T20 optoelectronic cameras (Vicon, Oxford Metrics, UK), which will be done both online with D-Flow software (Motek Medical BV, Amsterdam) as offline. Changes in the brain hemoglobin concentrations will be registered with a wireless 16-16 fNIRS system (NirXsports 2), which has the required resolution and coverage to meet the study objectives. Sixteen optodes per hemisphere will be placed over the prefrontal, posterior parietal and premotor, SMA and M1 regions with an inter-optode distance of 35 mm, placed on an EEG-cap using the 10-20/10-10/10-5 EEG system.

6 Statistics, data handling and data management

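### With a single printed block size of four, a tester who has seen every earlier arm would know one third of arms, on average, before the pre-test

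*Protocol*

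**What the plan says.** Protocol 5.3.1 (Design) gives the allocation rule in one sentence: "Randomization will be computer-generated and blocked in groups of four to achieve optimal distribution in each training arm". There are two arms, and Protocol 5.1 plans 20 per group, 40 in all, with more recruited if fNIRS data are lost. No stratification is mentioned.

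On who does what, Protocol 5.2 says: "The researchers responsible for testing will execute this recruitment process". Protocol 2.2 describes a "Monocentric study at the faculty of Movement and Rehabilitation Sciences", and Protocol 5.4 describes one CAREN system for the postural outcomes.

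On sequence, Protocol 5.3.2 says: "Before and after training, weight shifting ability will be assessed using the WASP-tests with and without serial subtractions". Protocol 2.4 places the pre-test and training in the same first session, "including 25 min of training". For the other arm, Protocol 5.3.2 says: "Subjects in the control group will not receive any form of training".

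The available text does not say who holds the list, whether an arm is released before or after the pre-test, or whether testers know it. The only mention of blinding is in the SAP (Main analysis), and it concerns the choice of covariates.

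**The concern.** Blocking in a single known size makes later places in each block deducible from earlier ones. Because controls receive nothing in place of training, anyone present on day 1 learns that participant's arm. With one size and one list, counting participants is enough to locate the block boundaries. A tester who runs the sessions in turn could therefore arrive at some pre-tests already knowing the arm, even if nobody has shown them the list.

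The pre-test is where this matters most. Write the main contrast (Protocol 6.2, SAP Main analysis) as

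(post_T − pre_T) − (post_C − pre_C).

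A stable difference b between the groups appears in both post_T and pre_T and cancels. A shift e that affects only the training group's pre-test does not cancel; it moves the contrast by −e. A tester who foresees the arm and encourages differently at the pre-test could produce such a shift. Selective booking is a weaker route: it would mostly create stable differences, and nothing in the documents suggests that a recruiter could judge who will improve.

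**Working it through.** **Inputs.** Block size four (Protocol 5.3.1); 20 per group, 40 in total (Protocol 5.1). Assumptions: two-and-two within each block, one unstratified list, and recruitment stopping at 40.

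**The plan's own figure.** 40/4 = 10 blocks, and 10 × 2 = 20 per group, which agrees with Protocol 5.1. The documents give no figure for predictability.

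**Fixed four, all earlier arms known.** There are six equally likely orders. TTCC and CCTT reveal places 3 and 4; the other four orders reveal place 4 only.
- Certain per block: (2 × 2 + 4 × 1)/6 = 4/3, so (4/3)/4 = 1/3 of arms.
- Over 10 blocks: mean 13.3, minimum 10 × 1 = 10, maximum 10 × 2 = 20.
- Best guess by place: 1/2, 2/3, 2/3, 1. Mean = 2.833/4 = 70.8%.

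**Fixed four, latest arm unknown.** Only place 4 can be certain, when places 1 and 2 match (probability 1/3).
- Certain: (1/3)/4 = 1/12 = 8.3%, or 3.3 of 40.
- Best guess by place: 1/2, 1/2, 2/3, 2/3. Mean = 2.333/4 = 58.3%.

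**Fixed four, latest two arms unknown.**
- Certain: 0%.
- Best guess by place: 1/2, 1/2, 1/2, 2/3. Mean = 2.167/4 = 54.2%.

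**Varied sizes 4, 6 and 8, chosen with equal probability.** These were simulated (3,000 lists of 40) against an optimal guesser who knows the set of sizes but not their order. A separate simulation of 4,000 lists with all earlier arms known gave 2.4% and 67.6%.

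| Earlier arms known | Fixed 4: certain / best guess | 4, 6, 8: certain / best guess |
|---|---|---|
| All | 33.3% / 70.8% | 2.3% / 67.6% |
| All but the latest | 8.3% / 58.3% | 1.5% / 59.4% |
| All but the latest two | 0% / 54.2% | 0.6% / 56.3% |

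**Cost in balance at 40.** Fixed four gives exactly 20/20. Under 4, 6 and 8, an exact recursion gives 20/20 in 72.5% of lists, 21/19 in 27.2% and 22/18 in 0.3%. Information relative to 20/20 is n1 × n2/400: 21 × 19/400 = 399/400 = 99.75%, and 22 × 18/400 = 396/400 = 99%.

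**The case against.** The strongest reply has four parts.

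- **Silence is not absence.** Some pages of the public documents are not available to read, and a release procedure may exist. This stands: a reader might infer that allocation is unconcealed, and the documents do not show that.
- **Full knowledge is an assumption.** Protocol 5.2 speaks of researchers in the plural, and no passage says that one person runs every session or that testers share arms. One CAREN system suggests sequential testing, not a single observer. This also stands. A reader might infer that testers will in fact know a third of arms, but that figure describes only a fully informed tester. For such a tester it is an average, not a ceiling, since the total can range from 10 to 20 of 40.
- **The outcome resists influence.** Speed is calculated from measured movement (Protocol 6.2, SAP Primary outcome) in short on-screen trials scaled to each person, and no encouragement is described. Instrument measurement does limit scoring bias. It does not limit effort, so the route is narrowed rather than closed.
- **Varied blocks achieve little.** A reader might infer that they stop guessing. They do not: with all earlier arms known, accuracy falls only from 70.8% to 67.6%, and with one or two arms unknown it rises slightly. What they remove is certainty, and mainly for the fully informed tester.

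**Conclusion.** The point holds as an inexpensive improvement to a stated rule. A printed fixed block of four, with testers who recruit and a visibly untreated control arm, leaves an avoidable risk of foreknowledge at the pre-test. For a tester who knows the boundaries and every earlier arm, the size is one third of arms on average; it shrinks quickly as recent arms become unknown. This rests on two-and-two blocks and one list; the counts out of 40 also require recruitment to stop at 40.

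A reader might go further and infer that the training effect is biased. The documents do not support that: no differential handling is described, stable baseline differences largely cancel, and neither the size nor the direction of any shift in m/s can be derived.

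**What to change.** 1. State that each allocation is released only after that participant's day-1 pre-test. The pre-test already precedes training, so the schedule does not change. For this to work, testers must not be able to see the list beforehand. If that is already the practice, one sentence records it; if not, someone else must hold the list, which is the only real staffing cost.
2. Replace the fixed block with randomly varied sizes, such as 4, 6 and 8, and keep the sizes out of the text that recruiters and testers see. Step 1 alone is not enough, because a fully informed tester can still deduce arms from a known fixed block. The cost is a new computer-generated list and the small loss of balance shown above.
3. Use one fixed instruction script for both arms at pre-test, post-test and retention. Steps 1 and 2 do nothing once the arm is known. The script limits differential encouragement but does not protect scoring of the MiniBEST, a tertiary outcome that is administered by a person and compared between pre-test and retention (SAP, Tertiary outcomes). That limitation should be acknowledged in the plan.
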